### 13.2 Informed Consent

All participants must be provided a consent form describing this study and providing sufficient information for participants to make an informed decision about their participation in this study. The formal consent of a participant, using the IRB approved consent form, must be obtained before the participant is involved in any study-related procedure. The consent form must be signed and dated by the participant or the participant's legally authorized representative, and by the person obtaining the consent. A remote consent can be obtained if the subject lives >50 miles from the treatment site. The informed consent document can be sent by facsimile and/or through a secure email account. The consent interview can be performed by telephone and a signed consent form can be returned to the clinical investigator by facsimile and/or through a secure email account to protect the confidentiality of the subject. The patient must be re-consented in

---

CONFIDENTIAL

*This document is confidential. Do not disclose or use unless authorized.*

person prior to starting treatment. The participant must be given a copy of the signed and dated consent document before participation in the trial. The original signed copy of the consent document must be retained in the medical record or research file.

The initial informed consent form, any subsequent revised written informed consent form and any written information provided to the subject must receive the IRB/ERC's approval/favorable opinion in advance of use. The subject or his/her legally acceptable representative should be informed in a timely manner if new information becomes available that may be relevant to the subject's willingness to continue participation in the trial. The communication of this information will be provided and documented via a revised consent form or addendum to the original consent form that captures the subject's dated signature or by the subject's legally acceptable representative's dated signature.

### **13.3 Ethics and Federal Regulations**

This study is to be conducted according to the following considerations, which represent good and sound research practice:

- US Code of Federal Regulations (CFR) governing clinical study conduct and ethical principles that have their origin in the Declaration of Helsinki
  - Title 21 Part 50 – Protection of Human Subjects  
[www.access.gpo.gov/nara/cfr/waisidx\\_02/21cfr50\\_02.html](http://www.access.gpo.gov/nara/cfr/waisidx_02/21cfr50_02.html)
  - Title 21 Part 54 – Financial Disclosure by Clinical Investigators  
[www.access.gpo.gov/nara/cfr/waisidx\\_02/21cfr54\\_02.html](http://www.access.gpo.gov/nara/cfr/waisidx_02/21cfr54_02.html)
  - Title 21 Part 56 – Institutional Review Boards  
[www.access.gpo.gov/nara/cfr/waisidx\\_02/21cfr56\\_02.html](http://www.access.gpo.gov/nara/cfr/waisidx_02/21cfr56_02.html)
  - Title 21 Part 312 – Investigational New Drug Application  
[www.access.gpo.gov/nara/cfr/waisidx\\_02/21cfr312\\_02.html](http://www.access.gpo.gov/nara/cfr/waisidx_02/21cfr312_02.html)
- State laws
- Institutional research policies and procedures:  
[www.dfhcc.harvard.edu/clinical-research-support/clinical-research-operations-cro/policies-and-procedures](http://www.dfhcc.harvard.edu/clinical-research-support/clinical-research-operations-cro/policies-and-procedures)

It is understood that deviations from the protocol should be avoided, except when necessary to eliminate an immediate hazard to a research participant. In such case, the deviation must be reported to the IRB according to the local reporting policy.

### **13.4 Study Documentation**

The investigator must prepare and maintain adequate and accurate case histories designed to record all observations and other data pertinent to the study for each research participant. This information enables the study to be fully documented and the study data to be subsequently verified.

---

*CONFIDENTIAL*

*This document is confidential. Do not disclose or use unless authorized.*

Original source documents supporting entries in the case report forms include but are not limited to hospital records, clinical charts, laboratory and pharmacy records, recorded data from automated instruments, microfiches, photographic negatives, microfilm or magnetic media, and/or x rays.

### **13.5 Records Retention**

All study-related documents must be retained for the maximum period required by applicable federal regulations and guidelines or institutional policies.

### **13.6 Cooperative Research and Development Agreement (CRADA)/Clinical Trials Agreement (CTA)**

Not applicable

## **14.0 STATISTICAL ANALYSIS PLAN**

### **14.1 Statistical Analysis Plan Summary**

The primary endpoint of this trial is to evaluate the overall response rate (ORR:CR+PR) via clinical assessment and/or RECIST criteria for adult patients with measurable disease on CT scan. A Simon two-stage design will be used to minimize the number of adult patients exposed to this regimen and the specific sample size and operating characteristics were chosen to be able to rule out a 15% response rate. The rate chosen for the null hypothesis is based on several considerations:

- 1) There is no effective therapy for the patient population in this protocol.
- 2) This protocol represents the first time that this patient population will receive a systemic treatment option.
- 3) The response rate observed using the regimen under study in this protocol in patients with HPV positive head and neck cancer [10] was 20% with corresponding exact 95% CI (5.7% to 43.7%) and although it is anticipated that the patients in this protocol with benign tumors could experience a higher RR since their tumors are chemotherapy and/or RT naïve, this is still unknown.

In the first stage, accrual will continue until 11 evaluable adult patients are entered. If there are  $\leq 1$  adult patients whose disease shows best overall response of CR/PR, accrual to this trial will be closed with the expectation that there is little evidence that the RR would reach 38%. The probability that the trial will close early is 49% if the true RR is 15%. If there are  $\geq 2$  adult patients whose disease shows best overall response of CR/PR, accrual will continue until a total of 21 adult evaluable patients who started protocol treatment are entered. If there are  $\geq 6$  adult patients among 21 evaluable whose disease shows best overall response of CR/PR, further testing of this regimen will be considered. If the true response rate is 38%, the probability of concluding the regimen is effective is 86%, if the true response rate is 15%, the probability of concluding the regimen is effective is 8%. Allowing 1 adult patient to not begin protocol

---

*CONFIDENTIAL*

*This document is confidential. Do not disclose or use unless authorized.*

treatment or be classified as ineligible, a total of 22 adult patients will be entered. In addition, approximately 2-3 pediatric patients will be entered as an exploratory cohort.

The primary efficacy population includes all eligible adult patients who begin protocol treatment. ORR will be summarized as a proportion with corresponding exact 95% confidence interval (CI) (if the trial closes to accrual after the first stage), or a corresponding 95% two-stage CI if the trial closes to accrual after the second stage. Best overall response for the pediatric patients will also be summarized.

Another endpoint is to assess adverse events. Adverse events will be classified and graded according to the CTCAE v.4.0. Frequencies of adverse events will be summarized overall and within adult and pediatric subgroups. Another endpoint is to assess quality of life (QOL). QOL will be assessed via self-report questionnaires at the timepoints outlined in the Study Flow Chart. Descriptive statistics from the questionnaires will be summarized across timepoints of assessment overall and within adult and pediatric subgroups. Rates of drop-out/non-response to QOL assessments and corresponding reason will also be summarized across timepoints of assessment. Secondary objectives include assessment of biomarkers in blood and tissue. Descriptive statistics from the assays will be summarized across timepoints of sample collection overall and within adult and pediatric subgroups. Rates of refusal and/or reason sample not obtained will be summarized across timepoints of assessment.

Various correlative studies will also be performed. Tissue and blood will be collected at baseline and at post-baseline timepoints as outlined in Section 9 and 10.1.2.7. Markers from tissue and blood will be summarized descriptively and graphically overall and within adult and pediatric subgroups. Within subject changes in markers will also be analyzed. Twenty-two adult patients with baseline and a post-baseline values provides 80% power to detect .65 SD mean difference (Wilcoxon sign rank test two-sided 0.05 alpha level). Baseline as well as changes from baseline to a post-baseline timepoint will also be compared between patients whose disease responded (CR,PR) and those whose disease did not respond using the Wilcoxon rank-sum test. Twenty two adult patients provides 82% power (using a two-sided 0.05 alphas level test) to detect a 1.4 SD difference in means assuming that 38% of the patients have disease which responds.

With an estimated monthly accrual of 1, the first stage is estimated to complete accrual in approximately 12 months. As is customary with this type of design, accrual will be suspended after the first stage (n=11 evaluable adult patients) in order to assess outcome, however, this suspension is also dependent on the actual observed accrual rate and the number of patients with best response confirmed for their disease while the first stage of the trial is accruing.

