## 1.0 TRIAL SUMMARY

Abbreviated Title	Phase II Study of pembrolizumab in Subjects with Human Papillomavirus-associated Recurrent Respiratory Papillomatosis
Trial Phase	II
Clinical Indication	The treatment of subjects with recurrent respiratory papillomatosis with extensive laryngeal, tracheal and/or pulmonary involvement
Trial Type	Interventional
Type of control	No treatment control
Route of administration	Intravenous
Trial Blinding	Unblinded Open-label
Treatment Groups	Pembrolizumab 200 mg every 3 weeks
Number of trial subjects	Approximately 22 subjects will be enrolled
Estimated enrollment period	Approximately 18-24 months
Estimated duration of trial	It is estimated that the trial will require approximately 60 months from the time the first subject signs the informed consent until the last subject's last visit.

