The goal of this study is to evaluate the efficacy of pembrolizumab in this patient population to support treatment with systemic immunotherapy which could minimize and/or eliminate the need for multiple surgical procedures over the patient's lifetime. The primary objectives of the trial are to determine the anti-tumor activity, safety, and tolerability of pembrolizumab treatment in male and female subjects diagnosed with RRP. Secondary objectives include evaluating the relationship between candidate efficacy/resistance biomarkers and anti-tumor activity and response duration of pembrolizumab. An exploratory objective is to assess the quality of life of RRP patients with pembrolizumab. Established quality of life is lacking in this patient population and, in a separate study, we are establishing baseline quality of life parameters of RRP patients being treated with standard of care, which is repeated surgeries.

[figure not shown]
The study will be conducted in conformance with Good Clinical Practices.

Specific procedures to be performed during the trial, as well as their prescribed times and associated visit windows, are outlined in the Trial Flow Chart – Section 9.0. Details of each procedure are provided in Section 10.0 – Trial Procedures.

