#### **3.3 Exploratory Objective & Hypothesis**

(1) **Objective:** To assess the quality of life (QOL) with immunotherapy treatment as compared to standard of care treatment in RRP patients.

**Hypothesis:** Treatment with intravenous administration of pembrolizumab improves the quality of life of RRP patients as compared to standard of care treatment, which is repeated surgical debridement over their lifetime.

---

*CONFIDENTIAL*

*This document is confidential. Do not disclose or use unless authorized.*

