 In subjects who discontinue study therapy without confirmed disease progression, a radiological and/or clinical imaging should be performed at the time of treatment discontinuation (i.e. date of discontinuation +/- 4 week window). If a previous scan was obtained within 4 weeks prior to the date of discontinuation, then a scan at treatment discontinuation is not mandatory.															
 In subjects who discontinue study therapy (early or at 24 months) without documented disease progression, every effort will be made to continue monitoring their disease status by radiologic imaging every 6 months (+/- 2 weeks) until: 1) documented disease progression; 2) death; or 3) 36 months post study registration, whichever occurs first.															
 Unresolved labs that are drug related AEs should be followed until resolution. Labs do not need to be repeated after the end of treatment if labs are within															

CONFIDENTIAL

*This document is confidential. Do not disclose or use unless authorized.*

Trial Period:	Screening Phase		Treatment Cycles								End of Treatment (early or at 24 months)	Post-Treatment		
			To be repeated beyond 8 cycles											
Treatment Cycle/Title:	Main Study Screening (Visit 1)	1	2	3	4	5	6	7	8	Discon	Safety Follow-up	Follow Up Visits 	Survival Follow-Up	
Scheduling Window (Days)  :		-28 to -1	$\pm 3$	$\pm 3$	$\pm 3$	$\pm 3$	$\pm 3$	$\pm 3$	$\pm 3$	At time of Discon	30 days post discon $\pm 2$ weeks	Every 8 weeks post discon $\pm 2$ weeks	Every 24 weeks $\pm 2$ weeks	

normal range.

Tumor biopsy will be obtained only if there are lesions present.

Tumor biopsy, blood for correlative studies for clinically stable subjects, and quality of life questionnaires should be obtained at treatment discontinuation.

Survival status should be obtained at each clinic visit and/or each tumor assessment. Following first disease progression, subjects will be followed by telephone for overall survival until death, withdrawal of consent, or 36 months from study registration, whichever occurs first.

Endoscopic evaluations at baseline should be done within 6 weeks prior to enrollment into the study.

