#### **10.1.2.8 Quality of Life Questionnaires**

Quality of life questionnaires will be completed prior to treatment and every fourth cycle thereafter until the end protocol treatment. (See Appendix F).

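### The exploratory quality-of-life hypothesis is comparative, but Section 14.1 plans only summaries by time point, with no within-patient change and no stated use of the separate standard-of-care study

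*Combined protocol and SAP*

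**What the plan says.** The hypothesis in Section 3.3 is comparative and directional: "Treatment with intravenous administration of pembrolizumab improves the quality of life of RRP patients as compared to standard of care treatment". The Trial Summary gives the type of control as "No treatment control", and all patients receive pembrolizumab. The only standard-of-care reference is outside the trial. Section 2.1 says that "in a separate study, we are establishing baseline quality of life parameters of RRP patients being treated with standard of care".

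Section 14.1 gives the QOL analysis in two sentences. The first is "Descriptive statistics from the questionnaires will be summarized across timepoints of assessment overall and within adult and pediatric subgroups". The second is "Rates of drop-out/non-response to QOL assessments and corresponding reason will also be summarized across timepoints of assessment". For tissue and blood markers, the same section plans an analysis of within-subject change and powers a signed-rank test for it.

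On timing, Section 10.1.2.8 says "Quality of life questionnaires will be completed prior to treatment and every fourth cycle thereafter until the end protocol treatment". Footnote 19 of the flow chart in Section 9.1 adds that "quality of life questionnaires should be obtained at treatment discontinuation". Section 9.2 schedules further forms for patients who are retreated. The flow charts show no QOL form in post-treatment follow-up. The VHI-10 is required only of patients enrolled once Amendment 10 was in force.

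**The concern.** A claim of improvement over surgery needs a contrast, and the QOL paragraph of Section 14.1 names none. It specifies no change from the patient's own pre-treatment score, no interval, no model, no missing-data method and no comparison with the separate study. The pre-treatment form is the closest internal reference, because it describes each patient while managed by surgery.

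Without within-patient change, the reader is left to compare means across time points. The patients who contribute to those means differ over time, for reasons linked to how they are doing. A drift in the mean could then be read as a treatment effect, or could hide one.

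**Working it through.** **1. Is there a QOL figure to reproduce?** No. The documents state no QOL effect size, SD, power or drop-out rate. The nearest figure is the marker power in Section 14.1: 22 adults, 0.65 SD, signed-rank test, stated power 80%. Simulation gives 80.2%. The plan thus already applies a paired analysis to data with the same structure and sample size.

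**2. Who contributes to each time point?** Treatment, and with it the four-cycle questionnaire schedule, can end for:
- confirmed progression (Sections 7.7 and 10.1.2.6.1, with exceptions for clinically stable patients);
- unacceptable adverse events (Section 7.7);
- a confirmed complete response after at least 24 weeks of treatment (Section 7.8).

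The first two tend to remove patients who are doing badly, the third patients who are doing well. Leavers give one form on leaving, but Section 14.1 does not say where that off-schedule score goes.

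**3. How far can selection move a mean when nobody changes?** Assume standardized normal scores with higher meaning better, a share f of patients lost from the bottom, and correlation c between the tendency to leave and the score. Then

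shift = c × φ(z_f) / (1 − f),

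where φ is the standard normal density and z_f its f-quantile.

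| f | φ(z_f)/(1 − f) | shift, c = 0.5 | shift, c = 1 |
|---|---|---|---|
| 20% | 0.2800/0.80 = 0.350 | 0.18 SD | 0.35 SD |
| 30% | 0.3477/0.70 = 0.497 | 0.25 SD | 0.50 SD |
| 40% | 0.3863/0.60 = 0.644 | 0.32 SD | 0.64 SD |
| 50% | 0.3989/0.50 = 0.798 | 0.40 SD | 0.80 SD |

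If the best-scoring patients leave instead, the sign reverses. At c = 1 the shift is −0.20, −0.35 and −0.50 SD for 10%, 20% and 30% loss.

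**4. Does paired change remove the problem?** A simulation used 22 patients, 9 of them lost, no true change, an assumed baseline-to-follow-up correlation of 0.6, and 20,000 runs. Entries are the spurious change in SD units for c = 0.5 and c = 1.

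| Loss driven by | Time-point mean minus baseline mean | Paired change, remaining patients only |
|---|---|---|
| Baseline score | 0.19; 0.38 | −0.13; −0.25 |
| Current score | 0.32; 0.63 | 0.12; 0.25 |
| Change itself | 0.14; 0.28 | 0.28; 0.57 |

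With a score at that time point from every patient, leavers included, the result is 0.00. Paired change in the remaining patients reduces the bias in some settings. It doubles it when loss depends on the change itself. The remedy therefore has to use the leavers' scores.

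**The case against.** The strongest reply is that this is an exploratory outcome in about 22 adults, with no planned QOL test and no decision rule, so descriptive reporting is defensible. That stands, and it fixes the severity.

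A reader might infer several stronger criticisms that the documents do not support:
- **Only patients still on treatment are measured.** A form is also due at discontinuation, and retreated patients complete more.
- **Attrition is ignored.** Rates and reasons are reported at each time point. This discloses selective loss, although it does not correct for it.
- **The baseline form goes unused.** The pre-treatment assessment is one of the summarized time points. What is missing is a statement that each patient's change from it will be reported.
- **Selection must look like improvement.** Patients with a confirmed complete response may stop, and some clinically stable patients with confirmed radiographic progression may continue. The net direction is unknown.
- **The objective can never be answered.** Section 2.1 also words the objective without a comparator, and says the questionnaires address preference relative to surgery. The Appendix F instruments are not reproduced in the text available here, so comparative items cannot be ruled out.

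It is also fair to say that the sizes above rest on assumption alone. What remains is that Section 14.1 gives markers a within-subject analysis, gives QOL none, and is silent on the separate study.

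**Conclusion.** The point holds as a mismatch between a comparative hypothesis and an analysis that names no contrast. Means by time point can also shift through selection, in either direction. Illustrative sizes are 0.18 to 0.80 SD upward if the worst-scoring 20-50% leave, and 0.20 to 0.50 SD downward if the best-scoring 10-30% leave.

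These figures rest on assumed loss shares, on c between 0.5 and 1 (c = 1 for the downward case), and on normal scores. They also treat leavers as contributing nothing at the time point, so they show what could happen rather than forecast this trial. They do not show that a rise in mean QOL would be spurious. Severity is minor.

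**What to change.** In Section 14.1:
- Report within-patient change from the pre-treatment questionnaire at each four-cycle assessment, with a 95% CI, from a repeated-measures mixed model using all available scores.
- State how the off-schedule discontinuation score enters, for example by actual time since first dose or by assignment to the next planned assessment. Say whether retreatment scores are kept separate.
- Add one simple sensitivity analysis for missing scores. The mixed model assumes that loss depends only on recorded data, and step 4 of the working shows that paired change in the remaining patients is not a safe substitute.
- Keep the planned table of drop-out rates and reasons.
- Restrict VHI-10 change to patients with a baseline VHI-10 form.

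In Section 3.3, reword the objective and hypothesis as change from the patient's own surgery-managed baseline. Label any comparison with the separate standard-of-care study as external and descriptive.

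The cost is a few sentences and a little more analysis work. No new data, visits or patients are needed.

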#### **10.1.2.7 Tumor Tissue Collection and Correlative Studies Blood Sampling**

The natural clinical course of these subjects is the need for repeated operative procedures to debride recurrent growths of papillomatous lesions which may block the airway. A baseline tissue sample prior to starting systemic treatment will be collected. Subsequently, a tumor biopsy of one progressing and/or one regressing lesion, whenever possible and at the discretion of the surgeon, should be obtained at each operative visit which will occur at a minimum of every 12 weeks (84 days +/- 7 days) while on the study. If there are no lesions in the upper aerodigestive tract at the time of the operative examination, a biopsy will not be obtained. Some patients may require more frequent debridements based on the clinical symptoms and at the discretion of the surgeon and biopsies will be obtained at each operative visit. The tumor samples will be evaluated for changes in expression of various immune biomarkers which will include, but are not limited to: PD-1, PD-L1, PD-L2, CD4, CD8, FoxP3, CTLA-4, Lag-3, Tim-3, IFN-g, and HPV-specific CD8+ T cells.

Blood for correlative biomarker studies will be collected at baseline, at each cycle which corresponds with an operating room visit, and upon disease progression. The blood will be evaluated for changes in circulating HPV-specific CD8+ T cells and cytokines. For those patients eligible for a Second Course Phase (Retreatment), blood will also be collected on day 1 of the first cycle of re-treatment.

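### The biomarker power figures assume 22 adults with complete samples; the plan targets 21 treated adults, and post-baseline tissue is missing once lesions have cleared

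*Combined protocol and SAP*

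**What the plan says.** Section 14.1 (Statistical Analysis Plan Summary) makes two power statements for the correlative markers, in tissue and blood together.

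- Within-patient change: "Twenty-two adult patients with baseline and a post-baseline values provides 80% power to detect .65 SD mean difference", with the test given as "Wilcoxon sign rank test two-sided 0.05 alpha level".
- Responders (CR or PR) against non-responders, by Wilcoxon rank-sum, for baseline values and for change from baseline: "Twenty two adult patients provides 82% power (using a two-sided 0.05 alphas level test) to detect a 1.4 SD difference in means". The split between the two groups rests on a response rate of 38%.

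The same section sets the second-stage target at 21 evaluable adults who started treatment. It reaches 22 by adding one: "Allowing 1 adult patient to not begin protocol" treatment or to be found ineligible.

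On tissue, footnote 18 of the flow chart in Section 9.1 says "Tumor biopsy will be obtained only if there are lesions present". Section 10.1.2.7 agrees: "If there are no lesions in the upper aerodigestive tract at the time of the operative examination, a biopsy will not be obtained". Blood is drawn at baseline, at cycles with an operating-room visit and at progression, with no condition on lesions. Section 14.1 commits to summarizing why samples were not obtained. It does not say which post-baseline sample enters the change analysis, or how patients whose lesions have cleared are handled.

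**The concern.** Two features of the design sit badly with a power statement that needs 22 complete pairs. One is small: the 22nd adult is there to absorb a patient who contributes no evaluable data. The other is structural. Complete response is defined in Section 10.1.2.6.1 as disappearance of all lesions, and no biopsy is taken when there are none. Post-baseline tissue can therefore be missing because of the outcome that defines the groups being compared.

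The first secondary objective (Section 3.2) is to relate immune markers to anti-tumour activity using pre- and on-treatment tissue. If cleared patients drop out of the tissue-change comparison, it has fewer responders than planned, and those who remain are mostly partial responders. The first effect costs power. The second changes what is being compared, in a direction the documents do not allow us to predict. Listing the reasons for missing samples discloses the gap but does not correct it.

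**Working it through.** **Inputs, all from Section 14.1.** Signed-rank: n = 22, shift 0.65 SD, two-sided 0.05, stated power 80%. Rank-sum: n = 22, difference 1.4 SD, 38% responders, two-sided 0.05, stated power 82%. Evaluable target: 21. Normally distributed data are assumed throughout.

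**Group sizes.** 0.38 × 22 = 8.36, so 8 v 14. 0.38 × 21 = 7.98, so 8 v 13.

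**Method.** Two routes were used.

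1. Noncentral t with the sample size multiplied by the Wilcoxon efficiency for normal data, 3/π = 0.955. The noncentrality is δ√(0.955n) for pairs and δ/√(1/(0.955n₁) + 1/(0.955n₂)) for two groups.
2. Simulation of the rank tests (200,000 trials per case), using exact critical values.

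**The plan's own figures.**

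- Pairs, n = 22: noncentrality 0.65 × √21.01 = 2.98, giving 80.9%. Exact test 80.4%. Stated 80%.
- Groups, 8 v 14: noncentrality 1.4/√(1/7.64 + 1/13.37) = 3.09, giving 83.3%. Exact test 80.8%; normal approximation to the rank-sum 83.0%. Stated 82%.

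Both reproduce within 2 points.

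**With 21 adults, all sampled.**

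- Pairs: noncentrality 0.65 × √20.05 = 2.91, giving 78.9%. Exact test 78.2%. The shift detectable with 80% power under the exact test is about 0.67 SD.
- Groups, 8 v 13: 82.1% by route 1, 80.1% by the exact test.

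The loss is about 2 points for pairs and about 1 for groups.

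**With k complete responders lacking post-baseline tissue.** Here k is an assumption. Pairs are 21 − k, and groups are (8 − k) v 13. Exact tests:

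| k | Pairs | Signed-rank power, 0.65 SD | Groups | Rank-sum power, 1.4 SD |
|---|---|---|---|---|
| 0 | 21 | 78.2% | 8 v 13 | 80.1% |
| 1 | 20 | 76.6% | 7 v 13 | 76.6% |
| 2 | 19 | 74.5% | 6 v 13 | 72.0% |
| 3 | 18 | 71.5% | 5 v 13 | 65.5% |
| 4 | 17 | 67.5% | 4 v 13 | 56.6% |
| 5 | 16 | 64.3% | 3 v 13 | 44.1% |

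The rank-sum column falls faster because every loss comes from the smaller group.

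**Which analyses the biopsy rule touches.** It affects change in tissue markers, and comparison of that change by response. It does not affect blood markers, or the baseline comparison of responders with non-responders.

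**The case against.** The best defence is that the plan's sentences are conditional and true. They say what 22 adults with both values would provide, and for 22 the figures are correct. A reader might infer a calculation error; there is none.

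Nor is 21 a ceiling. If all 22 adults entered are eligible and start treatment, all 22 can contribute, and Section 7.9 allows additional subjects. It would be wrong to conclude that the design cannot yield 22.

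A reader might also infer that responders as a class are lost from the tissue analyses. The documents do not support that. Partial response needs only a 25% fall in the summed score, so a partial responder still has lesions, and Section 10.1.2.7 asks for a regressing lesion where possible. Operative visits occur at least every 12 weeks, and the plan asks only for some post-baseline time point. A complete responder who still had lesions at an earlier operative visit can therefore supply a pair.

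Finally, no one can say from these documents that tissue power is any particular figure. Neither a complete-response rate nor a time to clearance is given. Losing 4 of 8 responders would mean that half were already clear at the visit analysed.

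These arguments stand, and they limit the size of the point. They leave three gaps: the stated power makes no allowance for missing samples, the post-baseline tissue visit is not named, and nothing is said about patients with no lesion left to biopsy.

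**Conclusion.** The concern holds in a limited form. For blood markers and baseline comparisons it amounts to 1 to 2 points of power and would not merit comment alone. For tissue change, the stated 80% and 82% hold only if no patient's sample is missing, and the biopsy rule makes some samples missing because of complete response. The loss could be slight (about 77% on either test with one patient missing) or substantial (about 64% paired with five missing, 57% rank-sum with four). Which applies depends on how many complete responders are clear at the analysed visit, and the documents do not say. The calculations also assume normal data, a 38% response rate and no other missing samples. The primary endpoint and the two-stage decision rule are untouched.

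**What to change.** Amend Section 14.1 as follows.

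1. Restate power for 21 adults: signed-rank about 78% at 0.65 SD (80% at about 0.67 SD); rank-sum about 80% at 1.4 SD for 8 v 13, exact test.
2. Give power for tissue change separately, as a sensitivity range labelled as an assumption. For example, with 1 to 5 of 21 adults lacking tissue, paired power is about 77% to 64%; rank-sum power is about 77% with 7 responders, 72% with 6 and 57% with 4.
3. Name the first scheduled on-treatment operative visit, at about week 12, as the post-baseline tissue time point. This fixes the choice in advance; it should not be justified by claiming that lesions are usually present then, which the documents do not show.
4. Report the number of complete responders absent from the tissue-change results beside those results.

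The cost is SAP wording and a less favourable stated power. No patients, samples or visits are added.
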